Outcome ascertainment will be performed in two ways. First, data elements within the PEDSnet common data model (CDM), which comprises structured data extracted from EHRs will be examined to identify the select medical events of interest. Each event will be defined using algorithms that will include diagnostic codes and if needed procedure and medication codes, recorded in the EHR. Second, because not all symptoms, signs, and health problems are included in the structured data as diagnosis codes, a chart review of the EHRs for all eligible study patients will be conducted to examine unstructured text data not captured in the CDM to identify additional patients with the select medical events of interest.

Patients with status epilepticus diagnostic codes in their record will be identified from the cohort and will have their results presented separately in sub tables. They will also contribute to the main study populations. This is to fulfill commitment to examine outcomes in SE patients when exposed to lacosamide. It is assumed that any patients treated with a loading dose of LCM will be more likely to be in SE and proving refractory to treatment than the usual seizure presentation in children.

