### 5.3.2 Baseline (pre-index) period

The baseline period for this study will be the 3 months prior to either the first newly initiated qualifying treatment episode of a higher IV LCM dose or a recommended initial IV LCM dose; for patients less than 3 months of age at index event, the baseline period will be birth through index event.

Data from the baseline period will be used to determine the indications for LCM and to define a new treatment episode. All available data prior to the index date will be used to evaluate the patient characteristics, diagnosis, procedures, and medications administered, dispensed or prescribed (AEDs, benzodiazepines and non-AEDs) medications, and identify preexisting

conditions of interest, if any. Preexisting medical events of interest are not exclusion criteria in this study; instead, they will be used to characterize the patient population. Section 5.5.6 details pre-existing medical events of interest that will be evaluated during the baseline period.

Potential indications for IV LCM include but are not limited to epilepsy, febrile seizures, and status epilepticus. The indications in both the higher and recommended IV LCM cohorts will be classified as follows:

- Patients with only one of the listed potential indications in the baseline period will be assigned the identified indication
- Patients with none of the listed potential indications in the baseline period will be classified as having other indications
- Patients with more than 1 of the listed potential indications in the baseline period will be classified as having multiple indications.

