#### 5.9.1.1 Adjustment for baseline characteristics using propensity scores

We will use propensity score and inverse probability of treatment weights (IPTW) to control confounding (Brookhart 2013). The propensity score will be estimated using a logistic regression model, in which higher IV LCM dose (vs. recommended initial/maintenance IV LCM dose) will be regressed on the baseline characteristics. Covariates for inclusion in the propensity score model were selected based on their potential association with the outcomes, including patient characteristics, patient disease history, and treatment history, as indicated on page 35 of the study protocol under section 5.6.6, and on page 21 section 5.6.3 of the protocol, and as listed below:

- Weight
- Sex
- Age at time of seizure treated with loading dose
- Ethnicity (if available)
- PEDSNet site
- Diagnosed medical conditions
- Prior AED/benzodiazepine prescribing (home use) or administration in hospital
- Prior seizure number if available
- Treatment for said seizures (AED and/or benzodiazepine)
- Concomitant prescribing
- Pre-existing medical conditions of interest for the safety evaluation: cardiac conditions, dermatologic conditions, vascular conditions, injury, poisoning and procedural complications, general disorders and administration site conditions, investigations, drug reaction with eosinophilia and systemic symptoms syndrome, severe cutaneous adverse reactions, hypersensitivity events
- Prior EEG data at last seizure

After the propensity scores have been generated, we will assess for violations of underlying assumptions. Positivity violations will be assessed by plotting the propensity score distributions in an overlay plot for the comparator groups. To evaluate adequate overlap of the propensity scores, we will visually inspect the density distribution of the propensity scores (Rosenbaum and Rubin, 1984). The performance of the model will be evaluated by assessing the covariate balance across the treatment groups. Standardized differences will be used to compare the mean or prevalence of baseline covariates between the comparator treatment groups in the samples

weighted by the inverse probability of treatment. Additionally, continuous variables will be compared using graphical methods including boxplots and nonparametric density plots.

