### 5.9.4 Strength and Limitations

**Unmeasured confounding:** As the study is comparing the incidence rates of select medical events in patients who are treated with a high dose of IV lacosamide to patients who are treated with recommended dose of IV lacosamide, the major confounders are factors that impact the incidence rate of these medical events of interest. These factors include age, gender, comorbidities, and exposure to other medications which are measured. Unmeasured confounding would only occur if there was a major confounder which is not measured and thus missed from the adjusted model. However, the electronic medical records include demographic information, the medical history of the patients and any medications prescribed by the physicians. Therefore we anticipate that information on most of the confounders will be available. It is possible that there will be missing information on some comorbidities, if they are not recorded by the physicians and on medications that are either bought over counter or prescribed outside the PEDSnet healthcare network. Nevertheless, most hospitals in the PEDSNet healthcare network are large with epilepsy comprehensive care centers within the neurology departments, so we anticipate reliable background medical. We do not anticipate that there will be a disproportionate difference in the recording of the medical history data and prescription of medications in patients who are treated with high dose lacosamide and recommended lacosamide prior to the index date. Therefore, we anticipate that there will be minimal unmeasured confounding. Additionally, the analysis will be using new user design to minimize confounding by indication.

**Reduced generalizability:** The PEDSnet database is restricted to subjects seeking and receiving medical care within a facility affiliated with PEDSnet. Data is obtained from multiple care sites and type (e.g. in-patient, out-patient, emergency department). However, if a report of an event was made or a subject was treated for an event at a facility that is not affiliated PEDSnet, this information will not be captured in the PEDSnet data. However, as most events are anticipated to occur within 24 hours of receiving IV LCM, the impact of this is likely to be low.

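### Residual confounding by status epilepticus and acute severity is likely in the pooled weighted IRR: care location is not in the propensity score and status epilepticus at the index dose is not cleanly captured

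*Protocol*

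**What the plan says.** - **Expected imbalance (5.1).** "It is assumed that any patients treated with a loading dose of LCM will be more likely to be in SE and proving refractory". Of the children with SE the section adds: "They will also contribute to the main study populations".
- **SE sub-tables (5.1).** "Patients with status epilepticus diagnostic codes in their record will be identified from the cohort". No time window relative to the index dose is given.
- **Indication (5.3.2).** "Data from the baseline period will be used to determine the indications for LCM and to define a new treatment episode". Epilepsy, febrile seizures and SE are named as possible indications. A child with more than one goes into a multiple-indications category. For a child with none: "Patients with none of the listed potential indications in the baseline period will be classified as having other indications".
- **Propensity score (5.9.1.1).** "Covariates for inclusion in the propensity score model were selected based on their potential association with the outcomes, including patient characteristics, patient disease history". The sentence goes on to treatment history, cites sections 5.6.6 and 5.6.3, and introduces a list. The list includes diagnosed medical conditions, prior antiepileptic or benzodiazepine treatment (home or hospital), prior EEG, and "Age at time of seizure treated with loading dose". It names neither SE nor care location.
- **Outcome model (5.9.1.1 and 5.9.1.5).** Weighted Poisson regression on exposure status alone.
- **Stratification.** Section 5.9 stratifies all analyses by indication and by ICU or other department, among other factors. The executive summary does so only if numbers allow.
- **Confounding by indication (5.9.4).** "the analysis will be using new user design to minimize confounding by indication". The section also expects little unmeasured confounding.

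**The concern.** The protocol names a severity difference between its two dose groups and then does not clearly put that difference into the adjustment. The outcomes include loss of consciousness, somnolence, bradycardia and cardiac arrest. Children in SE or intensive care can plausibly have these more often at any dose, and closer monitoring records more of them. If the weights do not balance SE and care location, part of the severity difference is read as a dose effect in the pooled IRR.

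The new-user argument does not close the gap. Both cohorts start the same drug, so restricting to new users does not balance the reason for choosing the higher dose. The SE sub-tables have a related problem. They are meant to meet a commitment on children in SE exposed to lacosamide, but an SE code long before or after the index dose would qualify a child for them.

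**Working it through.** **Step 1. What reaches the score.**
- *Care location.* It is absent from the 5.9.1.1 list. The cited numbers 5.6.6 and 5.6.3 do not exist; the matching headings are 5.5.6 and 5.5.3. Neither contains an ICU or ward variable. Section 5.9 uses care location as a stratifier, so the protocol treats it as available.
- *SE through indication.* Sections 5.5.6 and 5.5.3 include the indication for IV lacosamide, so SE can enter as one of its levels. A child coded with both epilepsy and SE becomes a multiple-indications case, and the SE information is lost.
- *SE through diagnosed medical conditions.* The item is not defined. Section 5.3.2 draws diagnoses from all data before the index date, so an old SE code could count as much as a current one.
- *SE sub-tables.* These use a code anywhere in the record, a third definition that is also not tied to the index dose.
- *Age.* The covariate in "Age at time of seizure treated with loading dose" is undefined for comparator children. Section 5.5.3 already has age at index date.

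**Step 2. What the model can correct.** Exposure is the only regressor, so a severity factor is adjusted in the pooled IRR only as far as the weights carry it, directly or by proxy.

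**Step 3. Illustrative size.** The protocol gives no SE prevalence by dose group, no effect of SE on event rates and no bias calculation, so there is no figure to reproduce. All inputs below are assumptions. The true IRR is 1, p1 and p0 are the SE prevalences in the high-dose and recommended-dose groups, and RR is the event rate ratio for SE versus no SE.

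With no adjustment, spurious IRR = [1 + p1(RR − 1)] / [1 + p0(RR − 1)].
- p1 = 0.6, p0 = 0.2, RR = 2: 1.6 / 1.2 = 1.33.
- p0 = 0.2, p1 from 0.4 to 0.7, RR from 1.5 to 3: from 1.2 / 1.1 = 1.09 to 2.4 / 1.4 = 1.71.
- p1 = 0.5, p0 = 0.4: 1.25 / 1.20 = 1.04 at RR 1.5, and 2.0 / 1.8 = 1.11 at RR 3.

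**Step 4. Adjusting on a mistimed SE flag.** Take p1 = 0.6, p0 = 0.2, RR = 2, 40% of children in the high-dose group, and a flag with the same sensitivity (Se) and specificity (Sp) in both groups.
- Flagged share in group g: f_g = p_g·Se + (1 − p_g)(1 − Sp). Overall: F = 0.4·f1 + 0.6·f0.
- True SE share among the flagged: p_g·Se / f_g. Among the unflagged: p_g(1 − Se) / (1 − f_g).
- Standardised rate, with RR = 2: F(1 + share among flagged) + (1 − F)(1 + share among unflagged).

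For Se 0.5 and Sp 0.9:
- f1 = 0.34, f0 = 0.18, F = 0.244.
- High dose: 0.244 × 1.882 + 0.756 × 1.455 = 1.559.
- Recommended dose: 0.244 × 1.556 + 0.756 × 1.122 = 1.228.
- Ratio: 1.27.

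| Se | Sp | Spurious IRR |
|---|---|---|
| 0.3 | 0.9 | 1.31 |
| 0.5 | 0.9 | 1.27 |
| 0.7 | 0.9 | 1.21 |
| 0.9 | 0.95 | 1.09 |
| 1 | 1 | 1.00 |

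The last row holds by construction.

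**The case against.** The strongest reply is that severity is already covered. The score is fitted on the baseline characteristics, and the misnumbered references bring in indication, of which SE is one level. The baseline window runs to the treatment episode, not to admission, so SE coded before the first IV dose can count. In-hospital antiepileptic and benzodiazepine treatment, prior seizure number, line of therapy and prior EEG all track refractoriness. Indication and ICU use are planned strata, and stratification is a recognised control for confounding. A separate analysis plan could set the SE code window.

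Much of this stands, and it rules out two stronger readings. A reader might infer that SE is missing from the score altogether and that the main confounder passes untouched into the IRR. The documents do not support that, because of the indication route and the proxies. A reader might also infer that any child whose first SE occurs in the index admission is classed under other indications. Section 5.3.2 does not say so. The doubt is narrower: Table 4 describes diagnoses as final encounter diagnoses, and the protocol does not say how these are ordered against the dose.

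The reply does not supply care location in the weights or recover SE from the multiple-indications category. The strata inherit the same indication variable, and the executive summary makes them conditional on numbers. The pooled IRR remains unstratified. Nor is this only detail for a later plan: section 5.9.1.1 says the covariates have been selected and lists them, and section 5.1 states the sub-table rule. The age covariate is a wording slip and is not expected to move the IRR.

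**Conclusion.** The point holds as residual confounding, not as absent adjustment. The protocol expects more refractory SE in the high-dose group, yet its score omits care location and captures SE at the index dose only in part. Its SE sub-tables need not describe children who were in SE when dosed.

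The size cannot be computed from the document. On the assumed 60% versus 20% with a rate ratio of 2, the spurious IRR is 1.33 with no adjustment and 1.09 to 1.31 with a mistimed flag. On 50% versus 40% it is 1.04 to 1.11 unadjusted. The unadjusted figures should not be read as the bias that the plan would leave, because the listed proxies will remove some of it. The upward direction assumes that SE raises the recorded event rate; for an outcome where RR is below 1, the same formula gives a bias below 1.

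**What to change.** - Add to the propensity score care location (ICU versus other) at the first IV lacosamide dose. Add also a separate yes/no indicator of SE in the index encounter at or before that dose, kept whatever other indications are coded. State how a diagnosis without a time is ordered against the dose.
- Define the SE sub-tables by the same indicator. Any SE code in the index encounter would be too wide, because it would admit SE that began after the dose.
- Replace the age covariate with age at index date, and correct the cross-references to 5.5.6 and 5.5.3.
- Reconcile the stratification statements in section 5.9 and the executive summary.
- Withdraw from section 5.9.4 the statements that a new-user design minimises confounding by indication between two doses of one drug and that unmeasured confounding will be minimal.

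The protocol already plans to use care setting, diagnoses and medications, so the cost is mainly specification and programming. The statistical price is less overlap in the propensity score and somewhat wider intervals.

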Then we will compute inverse probability of treatment weights, defined as the reciprocal of the probability of receiving the treatment that was actually received using the derived propensity score, to create a pseudo-population where the measured covariates are not associated with the outcome, and both cohorts are standardized to the overall population (Brookhart et al, 2013). Given IPTW is often hampered by extreme propensity scores, resulting in biased estimates and excessive variance, we will evaluate the distribution of the stabilized weights using graphical displays (e.g. boxplots) and descriptive statistics. The characteristics of the patients with outlier weights will be examined and if necessary, the model will be re-specified and the weights re-estimated, or if the outlier are not significant, symmetric trimming methods will be used to exclude these patients using  $\alpha = 0.1$  (cite Crump RK, Hotz VJ, Imbens GW, et al. Dealing with limited overlap in estimation of average treatment effects. *Biometrika*. 2009;96(1):187–199 ).

IPTW-weighted Poisson regression model with robust variance estimator (regressed on exposure status in the sample weighted by the IPTW) will be used to estimate adjusted incidence rate ratios and 95% CIs of each outcome. The advantages of IPTW weighting includes retention all study patients and estimation of an average exposure effect in the whole population of eligible patients as incidence rate ratio (IRR) the other propensity score methods require exclusion of patients who cannot be matched to a control. As this study is reliant on a relatively small population of pediatric patients, and where comparison is undertaken between groups, retaining all patients allows for greater power to investigate significant differences between groups. Use of an alternative matching method would also mean that the effect estimate obtained from the matching would only be generalizable to populations similar to the matched patients. Retention of all patients allows for greater generalizability to background populations.

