### **5.9.2 Handling of Missing Data**

Data is dependent on information that was recorded by physicians and nurses into the EHR. It is therefore assumed that the patient did not have the diagnosis of interest if it is not reported in the EHR. No missing data will be imputed. For demographic characteristics, the type of missingness will be evaluated.

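### Section 5.9.1.1 prefers IPTW because it keeps every patient and targets the whole eligible population, yet the same section allows symmetric trimming that would undo both

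*Protocol*

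**What the plan says.** All of the main text is in Protocol section 5.9.1.1.

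- **Target.** The weights are meant to give a pseudo-population in which "both cohorts are standardized to the overall population".
- **Exclusion.** The stabilised weights are to be inspected. If necessary the propensity model is re-specified; alternatively, where the outliers are judged not significant, "symmetric trimming methods will be used to exclude these patients using" α = 0.1.
- **Justification.** The next paragraph argues for weighting over matching: "The advantages of IPTW weighting includes retention all study patients and estimation of an average exposure effect in the whole population of eligible patients". It then rests two further claims on retention: "retaining all patients allows for greater power to investigate significant differences between groups" and "Retention of all patients allows for greater generalizability to background populations". Matching is criticised because its estimate would generalise only to patients like those matched.

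Section 5.9.1.4 lists the sensitivity analyses. None sets a trimmed result against an untrimmed one.

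On missing data, section 5.9.2 treats an unrecorded diagnosis as absent and adds: "No missing data will be imputed". The propensity covariates in section 5.9.1.1 include ethnicity, flagged as subject to availability, as well as "Prior seizure number if available" and "Prior EEG data at last seizure".

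**The concern.** Two adjoining paragraphs cannot both describe the same estimate. A trimmed analysis does not keep all patients, and its rate ratio belongs to the patients left after trimming. That is the limitation the protocol holds against matching.

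The condition for trimming makes this worse. It names no test, threshold or quantity that could be significant or not, so a reader cannot tell in advance which population the reported estimate will describe. If the effect of dose group differs between patients with moderate and extreme scores, the two populations have different rate ratios. The report would then attach a whole-population claim to the wrong one.

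**Working it through.** The protocol states no retained share, so there is no figure to reproduce. The contradiction itself needs no arithmetic; the calculation only shows how much could be at stake.

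**Inputs from the protocol.** α = 0.1 (section 5.9.1.1). A count of 875 children before the full criteria, several hundred expected afterwards, and no split by dose group (section 5.9.3).

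**Assumptions.**
- Trimming at 0.1 is read as keeping propensity scores e from 0.1 to 0.9. The protocol does not write this interval out.
- e is the probability of being in the smaller group, and logit(e) = a + s·x with x standard normal.
- For each assumed share π in the smaller group, a is solved so that the mean of e equals π.
- The share trimmed is P(e < 0.1) + P(e > 0.9).

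| Share in smaller group | s = 0.5 (c about 0.64) | s = 1 (c about 0.74) | s = 1.5 (c about 0.82) |
|---|---|---|---|
| 50% | 0% | 3% | 14% |
| 30% | 0.5% | 12% | 26% |
| 20% | 7% | 29% | 43% |
| 10% | 58% | 64% | 69% |

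On the full 875, 12.0% is 105 patients and 29.2% is 256. The analysis set will be smaller. The 10% row is an extreme case, since the average score then sits at the cut-off itself.

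**Who is removed.** In the 20%, s = 1 case, 29.2% of patients score below 0.1 and 0.006% above 0.9, so nearly all trimmed patients are those least likely to be in the smaller group. About 94% of those below 0.1 belong to the larger group. Their stabilised weight is 0.80/(1 − e), which lies between 0.80 and 0.80/0.90 = 0.89. Those are not outlying weights. So the score-based reading would mostly remove patients other than those with outlier weights, whom the sentence says it is about.

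**Change of target.** Take the same 20%, s = 1 case. Suppose the log baseline rate rises by 0.3 per unit of x, and the log rate ratio is log 1.5 + 0.3x. The whole-population rate ratio is 1.5 × exp(0.6²/2 − 0.3²/2) = 1.5 × exp(0.135) = 1.72. Averaged over patients with e from 0.1 to 0.9 it is 1.87. With a constant effect both equal 1.50, so the shift depends on the effect varying.

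**Missing covariates (conditional only).** If patients with an incomplete covariate were dropped, k covariates each missing independently in share m would lose 1 − (1 − m)^k. For k = 3 this is 14% at m = 5%, 27% at 10% and 49% at 20%. The protocol gives no missing shares and does not say that such patients are dropped.

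**The case against.** The strongest reply is that trimming is a fallback. The default is the full weighted sample, re-specification of the model is the other route, and if no outlier weights appear the retention statement is true as written. Inspecting weights uses treatment and covariates but not outcomes, so it is ordinary design-stage checking, not selection on results. The protocol also says that extreme scores cause bias and excess variance, so a trimmed estimate may be the more precise one. All of this stands. It makes the contradiction conditional but does not remove it, because the retention, power and generalizability sentences carry no qualifier for the case the previous paragraph provides for.

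It is also fair that the 0.1 to 0.9 interval is a reading of the text. The trimming percentages depend on it; the contradiction does not, since any reading excludes patients.

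Three stronger readings are tempting, and the documents do not support them.

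- **A large share will be lost.** Group sizes are unknown, and with 30% or more in the smaller group and weak prediction the loss is 0.5% or less.
- **The sickest children leave.** In the 20% case nearly everyone trimmed is unlikely to be in the smaller group, and the protocol does not say which group that is.
- **The no-imputation rule means complete-case deletion.** Section 5.9.2 does not say so. Unrecorded diagnoses count as absent, the availability wording could mean leaving a covariate out or giving it an unknown level, and EEG carries no such flag. The coding may also be set in an SAP not at hand.

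**Conclusion.** The point holds in a limited form. Section 5.9.1.1 claims retention of all patients and a whole-population effect, and also provides for excluding patients on a condition that cannot be interpreted. If trimming is used, the estimate applies to the overlap population only, and the stated grounds for preferring weighting over matching no longer hold for it.

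The size is unknown. Under a logit-normal score, the 0.1 to 0.9 reading and assumed group shares, the loss runs from near 0% (balanced groups, weak prediction) to about 29% (20% in the smaller group, c about 0.74), and to 43% at that share with c about 0.82. These are ranges under assumptions, not forecasts. The missing-covariate point is secondary and an inference only. The matter is worth correcting because it decides which population the reported rate ratio describes.

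**What to change.** In section 5.9.1.1:

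1. Always report the untrimmed stabilised-weight rate ratio, as the estimate that carries the whole-population claim.
2. Present any trimmed result beside it as a labelled sensitivity analysis, with the 0.1 to 0.9 interval written out, the number excluded per dose group, and the overlap population named as its target. Add it to the list in section 5.9.1.4.
3. Delete the condition that the outliers be not significant.
4. Limit the retention, power and generalizability wording to the untrimmed analysis.

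As a precaution, give ethnicity, prior seizure number and prior EEG a level for not recorded or none in the propensity model, and say so in section 5.9.2, so that no patient is dropped for a missing covariate.

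The cost is protocol or SAP wording and a small amount of programming. The drawback is that the untrimmed interval may be wider and more sensitive to extreme weights. Showing both results lets the reader see how much that matters.
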